9.4.3 ANALYSIS OF THE SECONDARY ENDPOINT(S)

Secondary assessments using similar measures will be administered at the end of each session to assess satisfaction with the content of each session (7 items, each measured on a 5-point Likert scale, where 1= Strongly disagree, 2= Disagree, 3= Neutral, 4= Agree, 5= Strongly agree; e.g. "I felt I could trust my group leaders"). We will calculate the mean scores for each sessions for youth and adults. The percentage of youth participants with mean score ≥ 4 and the percentage of adult participants with mean score ≥ 4 will be calculated (range 0-100%).

9.4.4 SAFETY ANALYSES

N/A

9.4.5 BASELINE DESCRIPTIVE STATISTICS

Summary statistics, including frequency tables, percentages, and proportions, will be used to describe participant demographic data and social network characteristics. Histograms, boxplots, quantile-quantile plots, and quantile-normal plots will be generated to visualize distribution functions and assess normality of quantitative data. Moreover, measures of center (mean, median) and measures of spread (standard deviation, range, interquartile range) will be calculated and presented. To assess differences at baseline between the youth in the experimental and control groups, demographics such as grade-level, race, and parental education will be compared while accounting for within-neighborhood clustering. Demographic variables resulting in between-arm imbalances will be considered as covariates in the primary and secondary analyses.

9.4.6 PLANNED INTERIM ANALYSES

N/A

9.4.7 SUB-GROUP ANALYSES

N/A

9.4.8 TABULATION OF INDIVIDUAL PARTICIPANT DATA

N/A

9.4.9 EXPLORATORY ANALYSES

As an exploratory measure, we will assess outcomes on the difference between pre- and post-intervention measures of social network metrics, including network size, density, and mean link strength, as well as violence perpetration, violence victimization, attitudes towards violence/retaliation, coping, and future orientation. We will utilize generalized linear mixed models to account for site-level clustering and include selected covariates. Missing data will be managed with multiple imputation if the mechanism of missingness is ignorable. Given the small sample and exploratory nature of the additional analyses, each exploratory test will utilize $\alpha=0.1$ for the threshold of significance, and no corrections will be made for multiple tests.

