6 STUDY INTERVENTION(S) OR EXPERIMENTAL MANIPULATION(S)

6.1 STUDY INTERVENTION(S) OR EXPERIMENTAL MANIPULATION(S) ADMINISTRATION

6.1.1 STUDY INTERVENTION OR EXPERIMENTAL MANIPULATION DESCRIPTION.

This pilot community-partnered cluster-randomized trial will examine the feasibility and acceptability of a social network-based youth violence prevention program called Strengthening Connections for Change for youth ages 13-17 and their self-identified key adult supports to focus on leadership, strengthening intergenerational networks, community engagement, and violence prevention. The study will be located in four lower resource Pittsburgh, Pennsylvania neighborhoods ('clusters') randomized to receive either the Strengthening Connections for Change program (i.e. intervention neighborhoods) or to a job skills training program (i.e. control neighborhoods). Randomization will occur 1:1 at the site level (2 intervention and 2 control sites). The study team will then work with each community-based site to recruit youth already engaged with the respective community site into the program to which each site has been randomized. The Strengthening Connections for Change intervention will be delivered weekly by research staff in twelve 2-hour sessions at community sites. The first 2 sessions will include youth-specific programming. For session 3-12, youth and adults will participate in separate programming for the first hour, then participate in a joint session.

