6.3 MEASURES TO MINIMIZE BIAS: RANDOMIZATION AND BLINDING

Assignment of Interventions: Randomization was performed at the neighborhood level. The initial randomization included 4 community-based sites. The study statistician performed this randomization as a one-to-one randomization between control and intervention arms.

Randomization was performed after approval for the study was obtained for a site in a new neighborhood so that the randomization assignment would not influence a site’s willingness to participate. Sites chosen for the program have participated in other studies and interventions prior to the implementation of SCC, so many of the sites and facilitators were familiar with the content and programming guidelines. Due to the study design, investigators, research staff, participants, facilitators, and community partners could not be blinded to intervention assignment.

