5. Change in violence perpetration: Summary score of past 30-day youth violence perpetration adapted from the Aggressive Behavior-SAGE Baseline survey (9 items, each measured on a 5-point frequency scale from 0 times to 7 or more times). Violence perpetration items will be added to create a summary violence perpetration score with 1 point for each response of at least 1 time (possible range: 0-9; lower score indicates better outcome). [Time Frame: Baseline, end of program (12 weeks)]

6. Change in violence victimization: Summary score of past 30-day youth violence victimization adapted from the Victimization-Problem Behavior Frequency Scale (9 items, each measured on a 5-point frequency scale from 0 times to 7 or more times). Violence victimization items will be added to create a summary violence victimization score with 1 point for each response of at least 1 time (possible range: 0-9; lower score indicates better outcome). [Time Frame: Baseline, end of program (12 weeks)]

7. Change in attitudes towards violence: Modified from the Children's Perception of Environmental Violence Scale, 6 items assessed on 5-point Likert scale, calculated as a mean score (possible range 1-5; lower score indicates better outcome). [Time Frame: Baseline, end of program (12 weeks)]

8. Change in coping: Modified from the Healthy Pathways Child-Report Scales: Active Coping Scale, 7 items assessed on 5-point Likert scale, calculated as a mean score (possible range 1-5; higher score indicates better outcome). [Time Frame: Baseline, end of program (12 weeks)]

9. Change in future orientation: Modified from the California Healthy Kids Survey, 7 items assessed on 5-point Likert scale, calculated as a mean score (possible range 1-5; higher score indicates better outcome). [Time Frame: Baseline, end of program (12 weeks)]

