9.4 STATISTICAL ANALYSES

9.4.1 GENERAL APPROACH

Descriptive statistics will characterize participants' demographics and baseline survey responses. T tests, Wilcoxon rank sum tests, and chi square tests will assess for differences in baseline characteristics and baseline survey responses among intervention versus control participants, after accounting for clustering. Feasibility and acceptability will be the primary outcomes of the pilot trial. Both feasibility/acceptability

and exploratory outcomes will be estimated within each study arm using point estimates and 95% confidence intervals. We will examine these endpoints separately for youth and adults. As an exploratory measure, we will assess outcomes on the difference between pre- and post-intervention measures of social network metrics, relationship quality and communication, attitudes towards violence, conflict resolution and coping, and future orientation between intervention and control participants. We will utilize generalized linear mixed models to account for site-level clustering. Missing data will be managed with multiple imputation if the mechanism of missingness is ignorable. Interview transcripts will be coded and analyzed by two independent reviewers through content analysis to identify themes related to intervention acceptability and satisfaction.

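### Should the exploratory youth comparisons adjust for each outcome's own baseline score instead of analysing the pre-to-post difference?

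*Combined protocol and SAP*

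**What the plan says.** Section 9.1 titles outcomes 4 to 9 as changes, each measured at baseline and end of program. Section 9.4.9 analyses them accordingly: "we will assess outcomes on the difference between pre- and post-intervention measures of social network metrics", with the violence, attitude, coping and future-orientation scores treated in the same way. The model is given in one sentence: "We will utilize generalized linear mixed models to account for site-level clustering and include selected covariates". Section 9.4.1 makes this a between-arm comparison, ending its list with "conflict resolution and coping, and future orientation between intervention and control participants". Adults are enrolled only in the intervention arm, so the comparison concerns youth.

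Two other sentences bear on covariates. Section 9.4.5 says "Demographic variables resulting in between-arm imbalances will be considered as covariates in the primary and secondary analyses"; this names neither the exploratory models nor baseline outcome scores. Section 9.4.1 says that tests "will assess for differences in baseline characteristics and baseline survey responses among intervention versus control participants, after accounting for clustering", but not what follows if a difference is found.

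**The concern.** Three features together look like a weakness.

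- **Known efficiency result.** With individually randomized participants, adjusting the final score for its baseline is at least as precise as analysing change. Change also over-corrects a chance baseline gap.
- **Baseline gaps are likely here.** There are two sites per arm. Staff "recruit youth already engaged with the respective community site into the program to which each site has been randomized", and "investigators, research staff, participants, facilitators, and community partners could not be blinded to intervention assignment". The arms may therefore differ at baseline by chance or through who chooses to join.
- **The covariate list is open.** A change score with its own baseline as a covariate gives, on an identity link, the same arm coefficient as a baseline-adjusted final score. If the baseline may be one of the covariates, both analyses fit the text, and an analyst could pick between them after seeing the results. Section 9.4.9 tests each outcome at 0.1 without multiplicity correction, which leaves further room for spurious signals.

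At stake is the quality of the preliminary estimates meant to inform a larger trial.

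**Working it through.** **The plan's own figure.** Section 9.2 gives one precision figure, a margin of error of no more than 0.20 for a proportion with 25 youth per arm. It reproduces without clustering: 1.96 × √(0.25/25) = 0.196. It concerns the primary outcomes and says nothing about change scores.

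**Inputs.** From the documents: 25 youth and two sites per arm, and an exploratory alpha of 0.1. Assumed, because the documents give none: within-site pre-post correlation r = 0.3/0.5/0.7, ICC, and correlation c of the site effects over time. Triplets below follow that order of r. Total SD is 1.

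**Step 1: independent youth.** The variance of the adjusted estimate relative to change is (1 + r)/2 = 0.65/0.75/0.85, so adjustment is 35/25/15% lower. This is the case that makes the concern look strong.

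**Step 2: four sites.** Simulated with sites of 13, 12, 13 and 12, Gaussian scores, a random site intercept fitted by REML and 20,000 replicates per cell:

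| ICC | c | adjusted/change variance |
|---|---|---|
| 0.05 | 0.5 | 0.70/0.77/0.83 |
| 0.05 | 0.9 | 0.86/0.89/0.93 |
| 0.10 | 0.5 | 0.74/0.77/0.82 |
| 0.10 | 0.9 | 1.02/1.00/0.97 |
| 0.10 | 1.0 | 1.18/1.11/1.07 |
| 0.15 | 0.9 | 1.18/1.06/1.01 |

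The gain shrinks and then reverses as site effects become larger and more stable.

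**Step 3: response to a chance baseline gap.** The slope of the change contrast on the gap is −[(1−c)·ICC/2 + (1−r)(1−ICC)/25] / [ICC/2 + (1−ICC)/25].

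- ICC 0: −0.70/−0.50/−0.30.
- ICC 0.05, c = 0.9, r = 0.3: −(0.0025 + 0.0266)/(0.025 + 0.038) = −0.46. The triplet is −0.46/−0.34/−0.22.
- ICC 0.10, c = 0.9: −0.35/−0.27/−0.18.

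The adjusted estimate errs the other way, by +0.24/+0.16/+0.08 at ICC 0.05 and +0.34/+0.23/+0.11 at ICC 0.10 (simulated, c = 0.9). At ICC 0.10 the two errors are of similar size.

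**Step 4: a recruitment difference.** Suppose the arms differ by a stable 0.3 SD at both times and there is no effect. Change cancels it. Adjustment removes only about r of it, leaving (1−r) × 0.3 = 0.21/0.15/0.09 SD. Simulated means agree within 0.01, and change stays within 0.005 of zero.

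**Step 5: false positives.** With no effect, c = 0.9 and a z-test at 0.1 (8,000 replicates per cell), rejection rates were:

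| ICC | adjusted | change |
|---|---|---|
| 0.05 | 11.4/11.0/11.3% | 9.0/9.6/10.5% |
| 0.10 | 14.0/13.0/13.2% | 10.4/11.5/12.6% |

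At c = 0.5 the two were similar.

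**Step 6: how far the two can disagree.** Their difference is roughly (1−r) times the baseline gap. The standard error of the gap is √[(2/25)(1 + 11.5·ICC)] = 0.35 SD at ICC 0.05 and 0.41 SD at ICC 0.10. With no true effect and c = 0.9, simulation puts the difference above 0.2 SD in 40/25/8% and 47/32/12% of trials respectively.

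**The case for a change.** The strongest opposing case does not depend on adjustment being better. It is that the wording leaves the choice open, and Step 6 shows that the choice matters: at r of 0.3 to 0.5, two analyses that both fit the text differ by more than 0.2 SD in a quarter to nearly a half of null trials. Naming the covariates and reporting both estimates would cost only words, since the baseline survey already collects the scores.

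The textual part stands: the covariates are unnamed and baseline handling is not stated. The freedom is narrower than it appears, though. Sections 9.1, 9.4.1 and 9.4.9 agree that the outcome is change, so the plain reading is a change contrast with a site effect. A baseline-adjusted result would have to be presented as an added covariate choice, and a reader would see it as one.

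A stronger remedy would make the adjusted final score the lead analysis. That does not stand, because it favours the estimator exposed to the unblinded recruitment that prompted the worry (Step 4). Nor is there support for a binomial model of each "summary violence perpetration score with 1 point for each response of at least 1 time (possible range: 0-9". It would treat nine items as independent and equally likely, which no section supports, and the calculations above are Gaussian only.

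**Conclusion.** No change is needed. The change contrast is a defensible exploratory analysis for this design, and replacing it would trade one exposure for another. With c = 0.9, adjustment has 14/11/7% lower variance at ICC 0.05, no material gain at 0.10 and 18/6/1% higher variance at 0.15. It also carries 0.21/0.15/0.09 SD of bias under a stable 0.3 SD recruitment difference. Every one of these figures rests on assumed correlations and ICCs, so the documents cannot settle which estimator is better.

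What remains is an unlisted set of covariates, which an analyst can fill sensibly: keep the stated change contrast and report which covariates were used. The consequence is small. Section 9.4.9 labels these tests exploratory, section 9.2 names the ICCs as the input to the future trial's sample size, and the primary outcomes are within-arm estimates of attendance and satisfaction that this model does not touch.

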10 SUPPORTING DOCUMENTATION AND OPERATIONAL CONSIDERATIONS

10.1 REGULATORY, ETHICAL, AND STUDY OVERSIGHT CONSIDERATIONS

10.1.1 INFORMED CONSENT PROCESS

10.1.1.1 CONSENT/ASSENT AND OTHER INFORMATIONAL DOCUMENTS PROVIDED TO PARTICIPANTS

Research assistants will provide an overview of what the research involves with youth who express interest during the initial conversation. Adults identified by youth will be given an overview of what the research involves during an initial conversation. Verbal informed consent from adults and informed assent from youth 13-17 will be obtained prior to the initial survey.

10.1.1.2 CONSENT PROCEDURES AND DOCUMENTATION

A waiver to document informed consent and a waiver for parental permission were granted by the IRB.

10.1.2 STUDY DISCONTINUATION AND CLOSURE

This study may be temporarily suspended or prematurely terminated if there is sufficient reasonable cause. Written notification, documenting the reason for study suspension or termination, will be provided by the suspending or terminating party to study participants, investigator, funding agency, and regulatory authorities. If the study is prematurely terminated or suspended, the Principal Investigator (PI) will promptly inform study participants, the Institutional Review Board (IRB), and sponsor/funding

agency and will provide the reason(s) for the termination or suspension. Study participants will be contacted, as applicable, and be informed of changes to study visit schedule.

Circumstances that may warrant termination or suspension include, but are not limited to:

- Determination of unexpected, significant, or unacceptable risk to participants
- Demonstration of efficacy that would warrant stopping
- Insufficient compliance of study staff to the protocol (ie, significant protocol violations)
- Data that are not sufficiently complete and/or evaluable
- Determination that the primary endpoint has been met
- Determination of futility

The study may resume once concerns about safety, protocol compliance, and data quality are addressed, and satisfy the funding agency, sponsor, IRB, Food and Drug Administration (FDA), or other relevant regulatory or oversight bodies (OHRP, DSMB).

10.1.3 CONFIDENTIALITY AND PRIVACY

Participant confidentiality and privacy is strictly held in trust by the participating investigators, their staff, the safety and oversight monitor(s), and the sponsor(s) and funding agency. This confidentiality is extended to the data being collected as part of this study. Data that could be used to identify a specific study participant will be held in strict confidence within the research team. No personally-identifiable information from the study will be released to any unauthorized third party without prior written approval of the sponsor/funding agency.

All research activities will be conducted in as private a setting as possible.

The study monitor, other authorized representatives of the sponsor or funding agency, representatives of the Institutional Review Board (IRB), regulatory agencies or representatives from companies or organizations supplying the product, may inspect all documents and records required to be maintained by the investigator, including but not limited to, medical records (office, clinic, or hospital) and pharmacy records for the participants in this study. The clinical study site will permit access to such records.

The study participant's contact information will be securely stored at each clinical site for internal use during the study. At the end of the study, all records will continue to be kept in a secure location for as long a period as dictated by the reviewing IRB, Institutional policies, or sponsor/funding agency requirements.

Study participant research data, which is for purposes of statistical analysis and scientific reporting, will be transmitted to and stored in the research team's secure, password protected electronic database. This will not include the participant's contact or identifying information. Rather, individual participants and their research data will be identified by a unique study identification number (using the secret code generated by participants).

Measures Taken to Ensure Confidentiality of Data Shared per the NIH Data Sharing Policies

It is NIH policy that the results and accomplishments of the activities that it funds should be made available to the public (see <https://grants.nih.gov/policy/sharing.htm>). The PI will ensure all mechanisms used to share data will include proper plans and safeguards for the protection of privacy, confidentiality, and

security for data dissemination and reuse (e.g., all data will be thoroughly de-identified and will not be traceable to a specific study participant). Plans for archiving and long-term preservation of the data will be implemented, as appropriate.

Certificate of Confidentiality

To further protect the privacy of study participants, the Secretary, Health and Human Services (HHS), has issued a Certificate of Confidentiality (CoC) to all researchers engaged in biomedical, behavioral, clinical or other human subjects research funded wholly or in part by the federal government. Recipients of NIH funding for human subjects research are required to protect identifiable research information from forced disclosure per the terms of the NIH Policy (see <https://humansubjects.nih.gov/coc/index>). As set forth in 45 CFR Part 75.303(a) and NIHGPS Chapter 8.3, recipients conducting NIH-supported research covered by this Policy are required to establish and maintain effective internal controls (e.g., policies and procedures) that provide reasonable assurance that the award is managed in compliance with Federal statutes, regulations, and the terms and conditions of award. It is the NIH policy that investigators and others who have access to research records will not disclose identifying information except when the participant consents or in certain instances when federal, state, or local law or regulation requires disclosure. NIH expects investigators to inform research participants of the protections and the limits to protections provided by a Certificate issued by this Policy.

10.1.4 FUTURE USE OF STORED SPECIMENS AND DATA

Data collected for this study will be analyzed and stored at the University of Pittsburgh in [name] (PI) research office, on a password protected secure drive. The research team will not make individual participant data (IPD) available to other researchers.

10.1.6 SAFETY OVERSIGHT

As a minimal risk study, safety oversight is under the direction of the PI and an internal safety monitoring group including the study coordinator and study statistician.

10.1.7 CLINICAL MONITORING

Extra precautionary measures are taken to protect the data, including the use of a personally created ID code to maintain anonymity of the survey data and an internal data safety and monitoring plan, which includes the following:

- Systematically review assessment materials to ensure that assessment is conducted appropriately and that participants disclosing abuse or violence during the course of taking the survey receive appropriate connection to violence-related services and that mandated reports are made by site personnel when appropriate.
- Systematically review notes from research assistants to ensure that participants experiencing distress are being connected directly with the site directors and youth workers, receiving educational materials, and being referred appropriately; this includes ensuring that all research assistants document asking each participant about emotional distress after completion of the survey.
- Monitor staff performance with regard to protection of privacy, confidentiality, maintenance of secure databases, and study procedures designed to reduce the risk of distress and potential breaches of confidentiality.
- Ensure that the PI, or a designated qualified individual, will be available in the case the research staff needs to report behaviors or comments made during a survey or other research activities.
- Review and report any adverse events associated with the study.

